5.0 Special Considerations

5.1 Health Insurance Portability and Accountability Act (HIPAA)

N/A

5.2 Family Educational Rights and Privacy Act (FERPA)

N/A

5.3 Code of Federal Regulations Title 45 Part 46 (Vulnerable Populations)

A. Special Populations

- Children: We will include infants and young children in our study. Given their young age, they will not be providing assent. However, their parents will provide informed written consent.

5.4 General Data Protection Regulation (GDPR)

N/A

5.5 NJ Access to Medical Research Act (Surrogate Consent)

N/A

6.0 Data Management Plan

6.1 Data Analysis

Cognitive testing: As mentioned previously, we will take detailed notes during the cognitive testing. The notes will be subsequently analyzed by members of the study team ([name] & [name]) by assessing common themes/patterns in the message comprehension. Summaries that describe the issues noted for each message and how they were addressed will then be prepared and discussed as a team, in an iterative way until the point of theoretical saturation.

cRCT: To estimate the impact of the mHealth messaging intervention on anemia and MAD, as well as our secondary outcomes, we will utilize a difference-in-differences approach. Linear regression models will be fitted for each outcome, with explanatory variables that include the intervention indicator, time (baseline and endline), and intervention by time interaction. The interaction term is of primary interest, as it summarizes mean changes in the outcome before and after the intervention in the treatment group compared with the control group. The intervention variable is as randomized (intention to treat). We anticipate that the parallel trend assumption will hold in this scenario since the various clusters and triads within clusters are similar to each other socio-economically; however, we will carefully test this assumption by applying the recently developed difference-in-difference model checklist⁴. We will analyze the data on the individual level and use generalized estimating equation (GEE) extensions of regression in SAS 9.4 to account for clustering. All models will adjust for sex of the child, socioeconomic status of the family and highest education completed by the mother. We will also conduct exploratory subgroup analyses based on baseline anemia status.

Process evaluation: A mixed-methods analysis of both the quantitative and qualitative process data will be led by [name], in collaboration with the Senegal team. Key themes generated from the qualitative data related to the implementation challenges and opportunities for scale-up in different contexts will be identified in the analysis, guided by the process evaluation framework for cRCTs.³³ Total costs of the intervention, as well as average costs per child in the experimental group, will be estimated over the period of the intervention implementation. Where possible, a cost consequence analysis will be conducted that compares the average cost per child in the experimental and usual care group against the health consequences.^{34,35}

Food environment data: We will use the food environment data to calculate the market food diversity index, the cost of health diet as well as the ProDesirability score for fruits and vegetables. These data will allow us to better understand the availability, affordability and acceptability of foods that our study participants have access to with the view to informing more comprehensive interventions in these communities.

6.2 Data Security

We will collect identifiers (names, telephone numbers and GIS coordinates) and these will be retained only until the study activities are completed and published. Individuals will be assigned personal identification numbers in order to protect their identity. cRCT data will be collected with a tablet using an electronic data collection platform such as ODK (<https://getodk.org>). All data collected in ODK is encrypted.

All electronic documents will refer only to the identification numbers and the names of the subjects will not be linked to their data at any time point.

We will have hard copies of consent forms and interview/meeting notes for our project. During transfer from the study collection site to the storage site, we will guarantee that the data collection forms and interview/meeting notes are kept secure by keeping them in the study team's possession during transport and not leaving them unattended in any vehicle. All audio recordings from the semi-structured interviews will be immediately uploaded to the PI's password-protected computer. None of the hard copies of data collection will contain names of participants during storage. Data will be uploaded, immediately after data collection to Rutgers Teams, as well as being saved on a password protected computer.

All interview notes and informed consent files will be stored at the IRESSEF office in Dakar in a locked file cabinet that only the study team will have access to. They will be scanned and saved on a password-protected computer as encrypted files/folders. Only members of the study team will have access to the study documents.

6.3 Data and Safety Monitoring

This intervention is minimal risk. For that reason, we have not included a DSMB.

A. Data/Safety Monitoring Plan

B. Data/Safety Monitoring Board Details

6.4 Reporting Results

A. Individual Subjects' Results

As part of the baseline and endline surveys for the cRCT we will conduct hemoglobin measurements of young children in order to assess their anemia status. We will immediately provide the parents with the results. In addition, any child who has severe anemia based on the hemoglobin results (hemoglobin measured <7g/dL) will be referred to a health post or community health worker. We have attached the referral sheet that we will use.

In addition, we will work with community health workers and health posts in our study communities to ensure that they have iron tablets in stock in the event that children are referred to the clinics.

B. Aggregate Results

[name] will create a short video that summarizes the findings which can help to disseminate the findings among participants with low literacy levels.

C. Professional Reporting

The results will be disseminated to the scientific community using a variety of methods (professional meetings and conferences, peer-reviewed journals, institutional press releases, progress and final reports to the NIH).

The Rutgers and IRESSEF team will work together to disseminate the study findings to key stakeholders, including the Ministry of Health, in Senegal. Policy briefs will be developed that describe the study findings as well as its value-for-money. The IRESSEF has a strong relationship with the Ministry of Health and will help facilitate the dissemination of the study findings through their existing networks. We will also work closely with the Senegalese National Council for Nutrition Development (*Conseil national pour le développement de la nutrition*), to disseminate the findings to Community Health Workers and NGOs working in the area of nutrition in Senegal.

D. Clinical Trials Registration, Results Reporting and Consent Posting

Given the nature of this study, it will be registered on Clinicaltrials.gov.

6.5 Secondary Use of the Data

We will not share the data with other researchers for secondary research purposes. As such, this language has not been included on the consent form.

7.0 Research Repositories – Specimens and/or Data

N/A

8.0 Approvals/Authorizations

We have obtained IRB approval from the Senegalese Ministry of Health. We have included these approvals in our updated submission.

Study Title: The Impact and Implementation of a Mobile Messaging Intervention to Improve Infant and Young Child Nutrition in Senegal

NCT Number: NCT05374837

Document date: 05/21/24

Document name: Statistical Analysis Plan

STATISTICAL ANALYSIS PLAN

Study outcomes: Table 1 provides an overview of our study outcomes.

Table 1. Overview of study outcomes

Outcome type	Outcome	Description
Primary	Anemia prevalence	We will use Hemocue Hb301 machines to measure hemoglobin levels in children in order to determine anemia prevalence using the WHO cut-offs: mild $10 \leq \text{hb} < 11 \text{ g/dl}$; moderate $7 \leq \text{hb} < 10 \text{ g/dl}$ and severe $\text{hb} < 7 \text{ g/dl}$. A finger prick will be used to obtain a drop of capillary blood that is placed on a cuvette and inserted in the Hemocue machine to obtain an on-the-spot assessment of hemoglobin levels.
	Minimum Acceptable Diet	Minimum Acceptable Diet Prevalence, Primary, baseline and endline: The minimum acceptable diet indicator will be used to assess dietary diversity in children. A 24-hour open dietary recall will be conducted with mothers to assess their child's dietary intake over the previous day. The 24-hour recall will be used to calculate minimum dietary diversity (MDD) (consuming ≥ 4 of 7 food groups (grains, roots and tubers; legumes and nuts; dairy products; flesh foods; eggs; vitamin A rich fruits and vegetables; other fruit and vegetables)) and minimum meal frequency (MMF) (2x/day for breastfed infants 6-8.9 months; 3x/day for breastfed children 9-23.9 months; 4x/day for non-breastfed children 6-23.9 months). Children who meet the thresholds for both MDD and MFF are defined as consuming a MAD, based on the WHO/UNICEF IYCF indicator.
Secondary	Frequency of consuming key foods in past 7 days	Frequency of consuming key foods in the past 7 days, Secondary, baseline and endline: We will use a 7-day food frequency questionnaire (FFQ) to assess the frequency that children consumed specific foods targeted in the intervention over the course of the previous week. More specifically, the FFQ will ascertain the number of times that the following foods have been consumed: eggs, leafy greens, fish, milk, cowpea, nuts, orange colored fruits and vegetables, other fruits and vegetables, thick porridge, beef or mutton, pork, chicken and liver.
	IYCF practices	IYCF practice indicators, secondary, baseline and endline: We will use the WHO/UNICEF IYCF indicators to assess feeding practices. Mothers will be asked about feeding practices as part of the household surveys. These include: Bottle feeding 0–23 months; Continued breastfeeding 12–23 months; Exclusive breastfeeding under six months; Exclusively breastfed for the first two days after birth; Egg and/or flesh food consumption 6–23 months; Early initiation of breastfeeding; Ever breastfed; Introduction of solid, semi-solid or soft foods 6–8 months; Minimum dietary diversity 6–23 months; Mixed milk feeding under six months; Minimum meal frequency 6–23 months; Minimum milk feeding frequency for non-breastfed children 6–23 months; Sweet beverage consumption 6–23 months;

		
Unhealthy food consumption 6–23 months; Zero vegetable or fruit consumption 6–23 months
 
The proportion of children being fed according to the detailed descriptions of these indicators will be assessed based on the WHO/UNICEF IYCF indicator manual.

	IYCF knowledge, attitudes, norms and intentions	
IYCF knowledge, attitudes, norms and intentions, Secondary, baseline and endline: IYCF knowledge, attitudes, norms and intentions will be assessed using survey questions based on the components of the intervention. Both mothers and fathers will be asked the survey questions as part of the household survey. The questions are grounded in the theory of planned behavior and based on previously published IYCF knowledge, attitudes, norms and intentions questions by Monterrosa et al.¹ The questions have been pilot tested by the project PI.

Table 2. Overview of statistical tests to assess intervention impacts on outcomes

Primary outcomes	
Outcome	Statistical approach
Anemia prevalence	difference-in-difference
Minimum acceptable diet (MAD)	difference-in-difference
Secondary outcomes	
Frequency of consuming key foods in past 7 days	difference-in-difference
IYCF practices	difference-in-difference
IYCF knowledge, attitudes, norms and intentions	descriptive statistics

Description of Statistical Approach: To estimate the impact of the mHealth messaging intervention on anemia and MAD, as well as our secondary outcomes, we will utilize a difference-in-differences approach. Linear regression models will be fitted for each outcome, with explanatory variables that include the intervention indicator, time (baseline and endline), and intervention by time interaction. The interaction term is of primary interest, as it summarizes mean changes in the outcome before and after the intervention in the treatment group compared with the control group. The intervention variable is as randomized (intention to treat). We anticipate that the parallel trend assumption will hold in this scenario since the various clusters and triads within clusters are similar to each other socio-economically; however, we will carefully test this assumption by applying the recently developed difference-in-difference model checklist⁴. We will analyze the data on the individual level and use generalized estimating equation (GEE) extensions of regression in SAS 9.4 to account for clustering. All models will adjust for sex of the child, and highest education completed by the mother. We will also conduct exploratory subgroup analyses based on baseline anemia status.

References

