Household survey: Consenting participants (mothers and fathers) will complete a household survey that will include information regarding demographics, household characteristics, household expenditures (including healthcare and food expenditures), food insecurity, and infant and young child feeding (IYCF) knowledge, attitudes, beliefs, norms, intentions and behavior. Either the mother or father will answer the questions related to demographics and household characteristics. Both mothers and fathers will separately answer IYCF knowledge, attitudes, beliefs, norms, intentions survey questions. Given that mothers are the primary caregiver of their young children, we will ask mothers to report on the frequency of consuming specific foods targeted in the intervention using a food frequency questionnaire (FFQ) as well as the list-based 24-hour dietary recall, described below. This is typical of collecting dietary data for infants and young children, given that the mother is generally the primary person feeding their children. This is particularly true in the Senegalese culture, where women are the primary caregivers of their

children. The enumerator will record all verbal answers to the household survey questions in an electronic tablet.

List-based 24-hour dietary recall: A list-based 24-hour dietary recall will be conducted with women to assess the dietary intakes of their children. This involves assessing whether their child consumed a list of foods and beverages (including breast milk) over the past 24 hours. Based on the dietary recall we will calculate the minimum acceptable diet (MAD) which measures the proportion of children aged 6-23 months who: had meal frequency the previous day that met the minimum standard for their age as defined by the WHO; AND consumed foods from at least 4 of the 7 food groups identified by the indicator.

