 - In the event that an infant/child has severe anemia, they will be referred to the local health post. Prior to engaging in data collection, members of our study team will alert the local health posts of our study so that they are aware that they may receive referrals due to anemia. This approach is based on the recommendations of our local partners in Senegal as well as the CNERS IRB board.

Intervention description: A mobile voice messaging intervention aimed at improving IYCF practices will be delivered to mothers and fathers will young children (6-23 months). Eight voice messages were developed based on our formative research in the study regions. The voice messaging is based on key messages booklets for infant and young child feeding from UNICEF and the Senegalese '*Conseil national pour le développement de la nutrition*' (National Committee for Nutrition Development), ensuring that the messaging is consistent with both global and local recommendations. The theoretical underpinning of the way the messages are scripted is the Theory of Planned Behavior (TPB).²⁰ Using the TPB as the basis for the message framing, which places importance on the caregiver's beliefs about the behavior, their perceived efficacy of performing the behavior and the perceived benefits of performing the behavior,²⁰ we developed and piloted 8 primary messages. The messages contain information about the benefits and consequences of the behaviors, with the view to change attitudes, beliefs, intentions, community norms and, ultimately, behavior. The content of the messages will include 8 scripted messages related to: breastfeeding until two years of age, consuming a variety of foods within a given meal, limiting highly processed foods, the importance of animal sourced foods, consuming vitamin A rich fruits and vegetables, consuming leafy greens, handwashing and feeding infants and young children fruits and vegetables produced and foraged by the household.

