In addition to the 8 scripted messages, we will send an additional 8 unscripted role modeling messages, that describe strategies used by "positive deviants" to successfully adopt the key targeted behaviors. The intervention will be delivered over a 16-week period, which falls within the duration observed in previously published IYCF messaging interventions that demonstrated positive impacts.¹⁰ One voice and one text message will be sent each week over the 16-week period, which is aligned with both the previously published literature¹⁰ as well as the community preferences identified through our formative work.

We will not provide participants with phones as part of this intervention. Cell phone ownership is very high in these communities. In most cases, adults have their own phones. In the event that the man or woman participating in the study do not have their own phone, we will ask them if there is a phone that they have access to in the household. In this situation, we will send the voice messages to that phone. However, if they do not have access to a phone we will not continue the recruitment process. There will be no costs to the participants receiving the messages. We will cover all costs of sending the messages and the minutes spent sending them. Using a combination of voice and text messages will enable us to ensure that messages reach phones in areas with poor mobile coverage, while also accounting for literacy levels. Baseline and endline surveys will be conducted in both the control and experimental groups. The control group will receive the 16 messages after the completion of data collection.

Randomization of intervention: Computer-generated random numbers will be used to randomize 104 villages in a 1:1 allocation, stratified by village size (number of households per village) and region (Thiès, Diourbel, Fatick), to receive either the intervention (experimental group) or usual care (control group). Randomization will be conducted following a baseline survey and, given the nature of the intervention, will not be blinded. The intervention will be delivered over a 16-week period.

Data collection for process and economic evaluation:

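### The milk-feeding indicator for non-breastfed children is given an arm comparison, although its endline denominator is set after randomisation and is one the breastfeeding message is meant to change

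*SAP*

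**What the plan says.** SAP Table 1 lists "Minimum milk feeding frequency for non-breastfed children" aged 6–23 months among 15 indicators in the IYCF-practices row, under the label "IYCF practice indicators, secondary, baseline and endline". The same row contains "Continued breastfeeding 12–23 months". SAP Table 2 gives the whole row one method, difference-in-differences. The SAP's description of the statistical approach specifies arm, time and their interaction, GEE for clustering, and adjustment for child sex and maternal education. It adds: "The intervention variable is as randomized (intention to treat".

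Protocol 1.3 A (intervention description) puts breastfeeding first in its list of message topics: "The content of the messages will include 8 scripted messages related to: breastfeeding until two years of age". On timing, the randomisation paragraph says: "Randomization will be conducted following a baseline survey and, given the nature of the intervention, will not be blinded". The dietary recall captures current breastfeeding, since it involves "assessing whether their child consumed a list of foods and beverages (including breast milk) over the past 24 hours".

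Neither document has a rule for indicators whose denominator is only part of the sample. There is no restriction by baseline status, no whole-sample version and no caveat.

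**The concern.** A difference between arms has a causal reading when the children compared were fixed by randomisation. Here the endline comparison is made among children who are not breastfed on the survey day, after one arm has had 16 weeks of messages that include a call to keep breastfeeding. The plan itself treats breastfeeding as something that may move, because continued breastfeeding is a listed outcome.

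If the message works, some children who would have been weaned under control drop out of the intervention-arm denominator but stay in the control one. The two non-breastfed groups are then different kinds of children. The indicator could suggest harm or benefit to milk feeding when no child's milk feeding had changed. The listed covariates and GEE do not correct for this.

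**Working it through.** The documents give no power, prevalence or expected effect for this indicator, so there is no stated figure to reproduce. The check covers structure first, then an illustration with assumed inputs.

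**1. When is the denominator fixed?** Randomisation follows the baseline survey (Protocol 1.3 A). Non-breastfed status at baseline therefore precedes randomisation, and status at endline follows it. The expected baseline difference between arms is zero, so any distortion of the endline difference passes straight into the arm-by-time interaction. Differencing does not remove it.

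**2. Formula, with no true effect on milk feeding.** Define:
- s: share of the control-type non-breastfed endline group that the message keeps breastfed
- pa: indicator rate in children non-breastfed under either arm
- ps: indicator rate in children weaned only under control

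Control rate = (1 − s) × pa + s × ps. Intervention rate = pa. Spurious difference = pa − [(1 − s) × pa + s × ps] = s × (pa − ps). This is zero if s = 0 or pa = ps.

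**3. Illustrative values (all assumed), in percentage points.**

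| pa / ps | s = 10% | s = 25% | s = 50% |
|---|---|---|---|
| 40% / 60% | −2 | −5 | −10 |
| 30% / 60% | −3 | −7.5 | −15 |
| 50% / 50% | 0 | 0 | 0 |
| 60% / 40% | +2 | +5 | +10 |

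**4. What limits s.** A child already weaned at baseline cannot be kept breastfed. Let q be the share of the control non-breastfed endline group weaned after baseline, and k the share of those whom the message keeps breastfed; then s = q × k. With a 20-point gap and k = 10–40%, q = 100% gives 2 to 8 points. With q = 50% (assumed), s is 5–20% and the bias is 1 to 4 points. The documents give neither q nor k.

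**5. Number of children.** 510 triads at 1:1 is 255 per arm. With 5% attrition (Protocol 1.5), 255 × 0.95 ≈ 242 per arm at endline. If 10–30% of control children are non-breastfed (assumed), that is 242 × 0.10 ≈ 24 to 242 × 0.30 ≈ 73. Multiplying by (1 − s) for s = 10–50% leaves about 12 to 65 in the intervention arm.

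**6. Worked example.** Assume 20% of control children are non-breastfed, s = 25%, pa = 40% and ps = 60%.
- As planned: control 0.75 × 40 + 0.25 × 60 = 45% of about 48 children; intervention 40% of about 48 × 0.75 = 36. Difference −5 points.
- All-children composite (breastfed, or met the milk minimum): control 80 + 20 × 0.45 = 89%; intervention 85 + 15 × 0.40 = 91%. Difference +2 points, all of it from breastfeeding.
- Only children non-breastfed at baseline: 0 points, assuming the message does not restart breastfeeding.

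**7. Random error beside the bias.** For 45% of 48 against 40% of 36, the 95% half-width is 1.96 × √(0.45 × 0.55/48 + 0.40 × 0.60/36) ≈ 21 points, before clustering.

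**8. Continued breastfeeding.** Children are 6–19 months old at baseline (Protocol 4.1 C). If ages are spread evenly over completed months, 6 of 14, or 43%, are under 12 months and have no baseline value for the 12–23-month indicator. Endline is planned for October after a May/June baseline, so the youngest are still under 12 months then. This loses information; it does not cause bias.

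**The case against.** Much can be said on the other side. Breastfeeding is one of eight topics, the exposure is 16 weeks, and no document gives a weaning rate or a pilot effect on breastfeeding. If the message does not alter weaning, or the children it keeps breastfed resemble the rest in milk feeding, there is no bias. The indicator is one of 15 in a secondary row, and Protocol 1.5 bases the sample size on anemia and MAD alone. In the worked example the 5-point bias lies well inside a half-width of about 21 points. All of this stands. It limits the size and importance of the point, but it does not supply the missing rule for the denominator.

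Four stronger readings are tempting, and the documents do not support them:
- **That the message does change the group.** The documents show intent only.
- **That the intervention arm will look worse.** The sign depends on whether pa or ps is larger, and neither is given.
- **That the SAP contradicts its own intention-to-treat statement.** That phrase describes the arm variable, which is as randomised; it says nothing about denominators.
- **That MAD shares the problem.** MAD and minimum meal frequency use breastfeeding status only to choose the threshold and keep every child in the denominator.

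Children being weaned between surveys is not a bias in itself either, since it happens in both arms. Nor is the 12-month floor on continued breastfeeding a planning error; it is part of the indicator as listed.

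**Conclusion.** The point holds as a conditional one. The plan makes an arm comparison in a subgroup that is defined after randomisation and that the intervention is intended to change, and it has no provision for this. Bias requires two things: an effect of the message on weaning within 16 weeks, and a difference in milk feeding between the children kept breastfed and the others. Under assumed inputs the bias runs from −15 to +10 points, including zero. If half of the endline non-breastfed group was weaned after baseline, 10–40% of those were kept breastfed and the gap was 20 points, it is 1 to 4 points in either direction. The documents fix neither size nor direction. Only this secondary indicator is affected; the primary outcomes are not exposed to this selection. The change is worth making because it is cheap and prevents a causal reading that the comparison cannot bear.

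**What to change.** 1. In SAP Table 2, separate this indicator from the rest of the row. Report it descriptively by arm and time with denominators shown, and draw no causal conclusion from it.
2. If an arm comparison is wanted, restrict it to children non-breastfed at the pre-randomisation baseline and state that the group is small.
3. For the breastfeeding message, add the proportion still breastfed at endline among children breastfed at baseline. Compare arms at endline with the same clustering adjustment. Keep the standard 12–23-month indicator beside it, and note that children under 12 months at baseline have no baseline value.
4. If a composite over all children is reported (breastfed, or met the milk minimum), call it a combined outcome. It mainly reflects breastfeeding and must not be presented as a milk-feeding effect.

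The cost is a few lines of SAP text and one or two variables derived from recall data already planned at both surveys. There are two downsides. The added outcome is not a standard indicator, and its endline-only comparison departs from the difference-in-differences used elsewhere. Also, the SAP is dated 05/21/24, after the planned October 2022 endline of an unblinded trial, so the addition should be labelled as made late.

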	IYCF practices	IYCF practice indicators, secondary, baseline and endline: We will use the WHO/UNICEF IYCF indicators to assess feeding practices. Mothers will be asked about feeding practices as part of the household surveys. These include: Bottle feeding 0–23 months; Continued breastfeeding 12–23 months; Exclusive breastfeeding under six months; Exclusively breastfed for the first two days after birth; Egg and/or flesh food consumption 6–23 months; Early initiation of breastfeeding; Ever breastfed; Introduction of solid, semi-solid or soft foods 6–8 months; Minimum dietary diversity 6–23 months; Mixed milk feeding under six months; Minimum meal frequency 6–23 months; Minimum milk feeding frequency for non-breastfed children 6–23 months; Sweet beverage consumption 6–23 months; Unhealthy food consumption 6–23 months; Zero vegetable or fruit consumption 6–23 months The proportion of children being fed according to the detailed descriptions of these indicators will be assessed based on the WHO/UNICEF IYCF indicator manual.
	IYCF knowledge, attitudes, norms and intentions	IYCF knowledge, attitudes, norms and intentions, Secondary, baseline and endline: IYCF knowledge, attitudes, norms and intentions will be assessed using survey questions based on the components of the intervention. Both mothers and fathers will be asked the survey questions as part of the household survey. The questions are grounded in the theory of planned behavior and based on previously published IYCF knowledge, attitudes, norms and intentions questions by Monterrosa et al. ¹ The questions have been pilot tested by the project PI.

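### SAP Table 2 gives only descriptive statistics for the secondary outcome on feeding knowledge, attitudes, norms and intentions, while the SAP text and protocol 6.1 give the secondary outcomes a difference-in-differences GEE model

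*SAP*

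**What the plan says.** The protocol (Table 1 in section 1.6) lists the outcome as "IYCF knowledge, attitudes, norms and intentions, Secondary, baseline and endline", and SAP Table 1 classes it the same way. SAP Table 1 adds: "Both mothers and fathers will be asked the survey questions as part of the household survey". Protocol 1.3, under the household survey, is more specific: "Both mothers and fathers will separately answer IYCF knowledge, attitudes, beliefs, norms, intentions survey questions". Section 1.3 also places baseline and endline data collection in both arms.

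On analysis, the SAP's Description of Statistical Approach covers anemia and minimum acceptable diet, and then says: "as well as our secondary outcomes, we will utilize a difference-in-differences approach". It continues: "Linear regression models will be fitted for each outcome". The effect of interest is the intervention-by-time interaction, and the analysts will "use generalized estimating equation (GEE) extensions of regression in SAS 9.4 to account for clustering". Protocol 6.1 says the same on each of these points.

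SAP Table 2, placed directly before that text, is titled "Overview of statistical tests to assess intervention impacts on outcomes". It names difference-in-differences for anemia, minimum acceptable diet, food frequency and IYCF practices. For knowledge, attitudes, norms and intentions it says "descriptive statistics".

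**The concern.** An analyst cannot carry out both instructions as the only plan for this outcome. Descriptive statistics are also not a test of impact, which is what the table's title promises.

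If the table governs, the report will hold summaries by arm and wave. A reader could compare them informally, but would have no estimate of the difference in change between arms, no interval around it and no allowance for village clustering.

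This matters for interpretation. Protocol 1.3 bases the messages on the theory of planned behavior: they are meant to shift attitudes, beliefs, intentions and norms, and through them behavior. This outcome measures most of that pathway. Without an estimate, a positive or null result on diet cannot be set against a measured change in what parents know or intend.

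**Working it through.** There is no figure in the plan to reproduce. The check is a comparison of the texts, followed by two counts.

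**Step 1. Method named for each outcome.**

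| Outcome | Class | SAP Table 2 | SAP text and protocol 6.1 |
|---|---|---|---|
| Anemia prevalence | Primary | Difference-in-differences | Difference-in-differences, GEE |
| Minimum acceptable diet | Primary | Difference-in-differences | Difference-in-differences, GEE |
| Frequency of key foods | Secondary | Difference-in-differences | Difference-in-differences, GEE |
| IYCF practices | Secondary | Difference-in-differences | Difference-in-differences, GEE |
| Knowledge, attitudes, norms, intentions | Secondary | Descriptive | Difference-in-differences, GEE |

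Four of five rows agree and one conflicts. Among the secondary outcomes, two of three agree and one conflicts.

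**Step 2. Is an exception stated anywhere?** The places where one could stand are Table 1 of each document, SAP Table 2, the SAP text and protocol 6.1. None excludes this outcome from the models or gives a reason for describing it only. The conflict lies inside the SAP as well as between the SAP table and the protocol.

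**Step 3. Would the data support the model?** The model needs both arms at both waves. Both documents schedule the outcome at baseline and endline, and protocol 1.3 collects both waves in both arms from both parents. No further data are needed.

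**Step 4. What is undefined if the model is fitted?** The documents refer to survey questions drawn from a published set and pilot tested. Protocol 1.9 says that the instrument was included in the IRB application. No scoring rule appears in either document, so the dependent variable is not yet defined.

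**Step 5. How many models?** Four named constructs × two parents = 8, taking one score per construct. Item-level analysis would add more.

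**The case against.** The best counter-argument is that the row is deliberate. The SAP paragraph repeats protocol 6.1 almost word for word; the visible change is that family socioeconomic status no longer appears among the adjustment variables. Table 2 has no counterpart in protocol 6.1, so it is the newer, outcome-by-outcome statement, and it sets this row apart from four others. A specific entry beside an inherited general sentence may well reflect a choice. In addition, Aim 1 and the hypothesis in protocol 1.1 concern practices, diet and hemoglobin, not knowledge or intentions. Describing a mechanism outcome is defensible.

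Much of this stands. Intent cannot be settled from the documents, and a declared descriptive approach would be acceptable. But the exception is not declared, and the general text admits none.

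A reader might infer more than the documents support:

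- **That the test was dropped after results were seen.** The SAP is dated 05/21/24 and endline was planned for October 2022, but neither document says when data were accessed or why the row differs.
- **That the trial's main findings are at risk.** The primary outcomes are treated alike in every place.
- **That clustering will be handled wrongly.** Descriptive tables make no inferential claim. What is lost is the estimate and its interval.

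**Conclusion.** The inconsistency is real and its reach is small. One of five Table 2 rows, and one of three secondary outcomes, carries a method that contradicts the SAP's own text and protocol 6.1. The consequence depends on which text is followed. Under the table, a declared secondary outcome has no clustering-adjusted between-arm estimate or CI. Under the text, the estimate exists and only the row is wrong. Primary analyses, power and sample size do not change either way.

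The conclusion rests on reading the general statements about secondary outcomes and about each outcome as including this one, which both versions of Table 1 support by classing it as secondary. Severity is low.

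**What to change.** Change the Table 2 row to the difference-in-differences GEE model already given in the SAP text and protocol 6.1. Report the intervention-by-time estimate with a 95% CI as a secondary result, separately for mothers and fathers, so that two correlated answers from one household do not enter the same model undefined. Keep the descriptive tables as support. Define the score for each construct in the SAP.

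The cost is one table row, a scoring definition and at least eight secondary models. With that many estimates, they should be read as supportive and not singled out. No new data are needed. Protocol 6.1 already prescribes the model, so fitting it is not a later addition; only scoring choices made after data access need to be labelled as such.

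If descriptive reporting alone is intended, state the exception and its reason in the Description of Statistical Approach, and draw no between-arm impact conclusion for this outcome. That costs a sentence or two.
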